4.7 COVID-19 and SARS-COV-2 Infection Surveillance and Counseling

The incidence rate of virologically confirmed COVID-19 cases occurring after study enrollment will be summarized for each cohort by study vaccine group and severity (severe vs. non-severe) as defined by FDA criteria for the mITT. The incidence rate will be calculated in person-days, where incidence rate is calculated as shown below:

Incidence rate = (COVID-19 cases) / (Number of Participants \times Timeframe).

The timeframes that will be considered are onset within first 14 days after receipt of the first study vaccination and onset 14 days after receipt of first study vaccine. Surveillance time will be censored at the time of first event or at the time of receipt of off-study COVID-19 vaccine (per mITT definition).

A sensitivity analysis will be repeated to include both suspected and confirmed cases of COVID-19 for each Cohort or Sub-cohort by study vaccine group.

Data collected in response to COVID-19 and SARS-CoV-2 infection surveillance questionnaires and counseling will be presented in participant data listings.

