4.2.3 Withdrawal of Participant From Study

Participants are free to withdraw from participation in the study at any time upon request, without any consequence.

A participant will be withdrawn from the study if any of the following occur prior to first administration of study vaccine:

- The participant requests to discontinue study participation.
- Study vaccine is not administered.

A participant may withdraw from the study at any time at his/her own request. Reasons for discontinuation from the study may include the following:

- Refused further follow-up
- Lost to follow-up
- Death

- Study terminated by the Sponsor
- Participant request
- Investigator request
- Protocol deviation
- Opportunity to receive an approved COVID-19 vaccine

For any participant terminating the study sooner than 60 days after last study vaccine administration, the following guidelines should be observed:

- The participant should also be reminded about use of highly effective contraception until 60 days following last study vaccine exposure.
- Any pregnancy occurring this window should be reported to the Sponsor as soon as feasible.
- Should the Principal Investigator (PI)/site become aware at any time of any death or pregnancy occurring in these participants it should be reported to Sponsor.

The following guidance applies for participants who choose to exit the study to receive approved COVID-19 vaccine (Note: Participants can continue to be followed for safety even if they receive an authorized COVID-19 vaccine.):

- The participant is advised to wait 4 weeks since the last study vaccination before seeking licensed vaccine.
- Should the former participant experience any severe or serious or concerning AEs following receipt of the approved COVID-19 vaccine, they should notify the site. These events would be collected as post-study AEs. The participant should also report these AEs to the vaccine provider.

The Investigator must capture the reason for withdrawal in the electronic Case Report Form (eCRF) for all participants.

If a participant withdraws from the study, he/she may request destruction of any remaining samples taken and not tested, and the Investigator must document any such requests in the site study records and notify the Sponsor or CRO accordingly.

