6.2 Study Assessments and Visits

6.2.1 Cohort A Visits

The Schedule of Assessments for Cohort A (including Sub-cohorts A1 and A2) is located in [Appendix 1](#).

Participants in Cohort A are followed for 12 months post-second dose of the study vaccine until Day 394. Study vaccines are administered on Days 1 and 29 where safety and immunogenicity assessments are also performed prior to administration of the study vaccine. Clinic visits including safety laboratories should occur 3, 7, and 28 days post-vaccination (Days 4, 8, 29, 32, 36, and 57). Clinic visits including blood collection to measure the participant's immune response to the study vaccine should occur on Days 15, 29, 43, 57, 119, 209, 299, and 394 (Final Visit).

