6.2.2 Cohort B Visits

The Schedule of Assessments for Cohort B is located in [Appendix 2](#).

Participants in Cohort 2 are followed for 12 months post study vaccine until Day 366. Study vaccine is administered on Day 1 where safety and immunogenicity assessments are also performed prior to administration of the study vaccine. Clinic visits including safety laboratories should occur 3, 7, and 28 days post-vaccination (Days 4, 8, and 29, respectively). Clinic visits including blood collection to measure the participants immune response to the study vaccine on Days 15, 29, 91, 181, 271, and 366 (Final Visit).

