6.3.1.2.15 Reporting Cases of COVID-19 or Asymptomatic SARS-CoV-2 Infection

All participants will be reminded to contact the site within 24 hours for any signs or symptoms of COVID-19 as well as any known exposure to SARS-CoV-2/COVID-19 (see also Section 6.7). For those participants who terminate the study early, participants are requested to continue to report these events to the site and as soon as possible for up to 12 months since the last study vaccine administration.

Any site that is made aware of a case of suspected COVID-19 or asymptomatic SARS-CoV-2 infection must be report this to the Sponsor or designee within 24 hours of Investigator notification.

For participants who describe symptoms of or exposure to COVID-19, the site will complete a dedicated eCRF. For participants who terminate early from the study without withdrawing consent, this information will be captured on a paper case report form (CRF) (located in the Investigator Site File), which should be emailed or faxed to the Sponsor or designee.

The reporting instructions, including the email address or fax number for submitting paper forms, can be found in the Investigator Site File for the study.

All events of COVID-19 will be reviewed by the Sponsor/designee to determine if the case definition of severe COVID-19 ([Appendix 7](#)) is met.

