4.2 Analysis Sets

The analysis sets are defined as follows:

- **Full Analysis Set (FAS):** the FAS includes all randomized participants. Assignment of participants to study vaccine group is based on the planned assignment.
- **Immunogenicity Analysis Set (IAS):** The IAS includes all randomized enrolled participants who meet the following criteria:
 - Receive the specified number of doses of the study vaccine to which they are randomly assigned, within the predefined window;
 - Have at least one valid and evaluable immunogenicity result after the specified study vaccine dose;
 - Have blood collection within an appropriate window after the specified dose; and

- Have no other major protocol deviations as determined by the Arcturus Therapeutics Medical Monitor that would require exclusion from the immunogenicity analysis set.
- Safety Set (SS): The SS includes all randomized participants who receive at least one dose of the study vaccine. Assignment of participants to study vaccine group is based on the study vaccine actually received.
- Modified Intent to Treat Analysis Set (mITT): The mITT set includes all eligible randomized participants who receive all protocol-required doses of study vaccine up to the evaluation timepoint concerned. This set excludes any participant that receives an off-study COVID-19 vaccine prior to the analysis timepoint. Assignment of participants to study vaccine group is based on the planned study vaccine assignment.

Data summaries to be presented on more than one analysis set will only be produced on both analysis sets if there is a difference in the analysis sets.

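### SAP 4.7 prints the COVID-19 incidence rate on a head count times a common window, which does not apply the censoring required in the same section

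*SAP*

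**What the plan says.** SAP 4.7 plans a rate of virologically confirmed COVID-19 for the mITT set, by vaccine group and severity, in person-days. The printed definition begins "Incidence rate = (COVID-19 cases) / (Number of Participants" and multiplies that head count by a timeframe. The timeframes are "onset within first 14 days after receipt of the first study vaccination and onset 14 days after receipt of first study vaccine". The censoring rule follows: "Surveillance time will be censored at the time of first event or at the time of receipt of off-study COVID-19 vaccine (per mITT definition".

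The mITT set is defined in SAP 4.2. Membership is tied to the time point being evaluated, and on off-study vaccine the text reads: "This set excludes any participant that receives an off-study COVID-19 vaccine prior to the analysis timepoint".

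The protocol sets the length of follow-up. Section 6.2.2 (Cohort B) says that participants "are followed for 12 months post study vaccine until Day 366", and section 6.2.1 says: "Participants in Cohort A are followed for 12 months post-second dose of the study vaccine until Day 394". SAP 4.7 does not carry either day over as the end of the later window.

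Off-study COVID-19 vaccine is prohibited during the study (Protocol 5.7.2), but Protocol 4.2.3 foresees it: "Participants can continue to be followed for safety even if they receive an authorized COVID-19 vaccine". For those who terminate early, Protocol 6.3.1.2.15 says that "participants are requested to continue to report these events to the site and as soon as possible for up to 12 months" after the last dose. SAP 4.7 does not say whether such reports enter the rate.

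**The concern.** The formula and the censoring sentence give different instructions. A head count times a fixed window credits every participant with the whole window. Censoring credits each participant only with the days before a first event or an off-study vaccine. The two agree only if nobody in the arm is censored before the window ends, so a single case already separates them. A participant whose first event falls in the first 14 days would also still be counted in full in the later window's denominator.

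The reference to the mITT definition adds to this. SAP 4.2 removes a participant; it does not stop that participant's clock. If membership were fixed once, at the end of the study, anyone vaccinated off study would drop out together with any earlier case and all earlier days at risk. SAP 4.7 does not name the analysis timepoint that would settle this.

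What is at stake is the correctness and reproducibility of a reported rate: two programmers, each following a different sentence of SAP 4.7, would get different numbers. No test or decision depends on the rate.

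**Working it through.** The documents give no event count, attack rate or off-study vaccination rate, so there is no plan figure to reproduce. All counts and timings below are assumptions.

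**Arm sizes (SAP 3.1).** Cohort B: 36/3 = 12. Sub-cohort A1: 12/3 = 4. Sub-cohort A2: 24 × 3/4 = 18 (ARCT-154) and 24 × 1/4 = 6 (ARCT-021).

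**Later window.** Taking the nominal final visit as its end, Cohort B runs from Day 15 to Day 366: T = 366 − 15 + 1 = 352 days.

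**One censored participant.** If one of N participants is censored at a fraction u of the window, the summed days are T × (N − (1 − u)). The printed formula uses T × N. It therefore understates the rate by (1 − u)/N, whatever T is.

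| Arm size | u = 0.25 | u = 0.50 | u = 0.75 |
|---|---|---|---|
| 18 | 4.2% | 2.8% | 1.4% |
| 12 | 6.3% | 4.2% | 2.1% |
| 6 | 12.5% | 8.3% | 4.2% |
| 4 | 18.8% | 12.5% | 6.3% |

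**A busier arm.** Cohort B arm of 12 with 3 cases and 2 other participants vaccinated off study, all at mid-window (176 days):

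- Summed days at risk: 3/(7 × 352 + 5 × 176) = 3/3344 = 0.90 per 1000 person-days.
- Printed formula on all 12: 3/(12 × 352) = 3/4224 = 0.71 (−21%).
- The 2 vaccinees excluded as of end of study, printed formula: 3/(10 × 352) = 3/3520 = 0.85 (−5%).
- The same exclusion, individual days: 3/(7 × 352 + 3 × 176) = 3/2992 = 1.00 (+12%).
- Time-updated mITT membership, individual days: 0.90, no difference from censoring.

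**Worst case for exclusion, by construction.** Let one of the 3 cases be infected at quarter-window (88 days) and vaccinated off study later. The other 2 cases and 1 other vaccinee leave risk at mid-window. Summed days give 3/(8 × 352 + 88 + 3 × 176) = 3/3432 = 0.87. End-of-study exclusion loses that case: 2/3520 = 0.57 (−35%) with the printed formula, or 2/(8 × 352 + 2 × 176) = 2/3168 = 0.63 (−28%) with individual days.

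**Sampling error for scale.** The exact Poisson 95% interval on 3 cases is 0.62 to 8.77, that is −79% to +192% around the estimate.

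**The case against.** The strongest answer is that SAP 4.7, read as a whole, already means person-time. It gives the unit as person-days and speaks of surveillance time being censored, a sentence that would have no effect under a fixed denominator. The formula is then shorthand. That is the likelier intention, but it must be inferred against a written formula whose second factor is spelled out as two common windows.

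On the mITT set, membership depends on the time point, and SAP 4.7 itself says that time stops at vaccination. Applied over time, exclusion acts much like censoring. The parenthesis also reads most naturally as covering only the off-study vaccine clause. This stands, and it reduces the mITT issue to an unclear cross-reference.

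Off-study vaccination should also be uncommon: planning it is an exclusion criterion (Protocol 4.1.2), receiving it on study is prohibited, and leavers are advised to wait 4 weeks after the last study vaccination (4.2.3), so the first 14 days are barely affected. This limits the vaccine part but does not rescue the formula, because a first event is enough to trigger censoring.

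Finally, the endpoint is exploratory, no formal comparison between groups is planned, and the surveillance data are also listed by participant. These points stand and limit the harm.

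**Conclusion.** The point holds as a minor defect of specification. The printed formula does not apply the censoring required beside it, and its later window has no end. With one participant censored at mid-window, the understatement is 2.8% to 12.5% across arms of 18 down to 4. With 5 of 12 censored at mid-window it is 21%. These sizes rest on assumed counts and timing, and sampling error is much larger.

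Three stronger readings are tempting and are not supported:

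- A reader might infer that the sponsor intends a fixed denominator and will report wrong rates. The person-days unit and the censoring sentence point the other way; the text is ambiguous.
- A reader might infer that the mITT rule discards cases, as in the −35% and −28% figures. Those figures need membership fixed at end of study and a case in a later vaccinee. The first is only one possible reading, and the documents do not state it.
- A reader might infer that cases reported after early termination must be counted. Protocol 6.7 gives referral for medical follow-up as the purpose of that reporting, so ending surveillance at study exit would be a legitimate choice. The SAP only has to state it.

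The definition of a confirmed case, the censoring of titres after infection and the nucleocapsid sensitivity analysis concern other rules and form no part of this point.

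**What to change.** In SAP 4.7:

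1. Replace the denominator with the sum, over participants, of individual days at risk within each window. Each participant's time ends at the earliest of first event, off-study COVID-19 vaccine, or end of that participant's surveillance (last contact, at most the Final Visit: Day 366 for Cohort B, Day 394 for Cohort A). This also gives the later window an end.
2. State that, for this analysis, off-study vaccinees are censored at vaccination and not excluded. Delete the reference to the mITT definition or amend SAP 4.2 to match.
3. Say in one line whether cases and days reported after early termination count.

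The cost is a few sentences and a small change to the derivation. It uses the dates of first event, off-study vaccination and last contact. If post-termination reports are to count, the paper forms foreseen in Protocol 6.3.1.2.15 are needed as well. No new visits or assessments follow. SAP 1 allows amendment for Cohort A before database lock; if the Cohort B analysis plan is already final, the same definition can be documented in the clinical study report as SAP 1 provides.

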4.8 Statistical/Analytical Issues

4.8.1.1 *Adjustments for Covariates*

There are no planned applications of covariate adjustments; all statistical results are descriptive in nature.

4.8.1.2 *Handling of Dropouts or Missing Data*

No imputations will be performed on missing data for immunogenicity analyses; all analyses will be based on observed data only. Handling of missing adverse event or concomitant medications is described in [Section 4.6.2](#) and [Section 4.6.5.5](#) respectively.

4.8.1.3 *Interim Analyses and Data Monitoring*

There are no interim analyses planned, although an optional interim analysis is permitted by the protocol.

4.8.1.4 *Multicenter Studies*

This is a multicenter study, with approximately 4 sites expected to participate. Immunogenicity data collected from all study sites will be pooled for data analysis. The effect of study site on the analysis results may be explored post-hoc, as needed.

4.8.1.5 *Multiple Comparisons/Multiplicity*

There will be no adjustments for multiple comparisons in the immunogenicity analyses for this study. Results are descriptive in nature and there will be no formal comparisons made among study vaccine groups.

4.8.1.6 *Active-Control Studies Intended to Show Equivalence*

This study does not include an active-control product and is not intended to demonstrate equivalence between any two drug products.

4.8.1.7 *Examination of Subgroups*

Participants who have a nucleocapsid (N) binding antibody test that is positive during the study will be identified, and the immunogenicity analyses may be repeated for participants with and without this positive test, as applicable (for participants who are seronegative at baseline).

4.9 **Determination of Sample Size**

No formal sample size calculation was performed. Based on experience in the ARCT-021-01 study, the size of individual study vaccine groups was considered sufficient to meet the objectives of the study while minimizing unnecessary participant exposure.

4.10 **Changes in the Conduct of the Study or Planned Analyses**

There were no changes to the study conduct or planned analyses identified within the development of this SAP, relative to the descriptions provided within the clinical study protocol.

One clarification to the planned analyses is that the protocol stated that the MNT assay could include the ancestral strain, if available. The ancestral strain was not available and therefore not included as part of the planned analysis.

